# **VERSION HISTORY**

SAP Version	Date	Change	Rationale
1.0	02JUN2023	Not applicable	Original version

# LIST OF ABBREVIATIONS

AE	Adverse Event	
ATC	Anatomical/Therapeutic/ Chemical	
CCG	eCRF Completion Guidelines	
CRF	Case Report Form	
CSR	Clinical Study Report	
CTCAE	Common Terminology Criteria for Adverse Events	
DMP	Data Management Plan	
eCRF	electronic Case Report Form	
ICH	International Council for Harmonisation	
IND	Investigational New Drug application	
iPGA	intertriginous Physician Global Assessment	
ITT	Intent-To-Treat	
LOCF	Last Observation Carried Forward	
MedDRA	Medical Dictionary for Regulatory Activities	
OC	Observed Cases	
PGA	Physician Global Assessment	
PSO	Plaque Psoriasis	
PT	Preferred Term	
QD	Once a Day	
SAE	Serious Adverse Event	
SAP	Statistical Analysis Plan	
SD	Standard Deviation	
SoA	Schedule of Activities	
SOC	System Organ Class	
SOP	Standard Operating Procedures	
TEAE	Treatment-Emergent Adverse Event	
TLF	Tables, Listings, and Figures	
USA	United States of America	
USPI	United States Prescribing Information	
VTAMA	tapinarof	
WHO	World Health Organization	

## 1. INTRODUCTION

This statistical analysis plan (SAP) for the final analysis is based on the most recent approved clinical study protocol (Version 1.0 dated on 14 October 2022), electronic case report form (eCRF) (Version 1.1 dated on 09 February 2023), eCRF completion guidelines (CCG, Version 2.0 dated on 10 March 2023), and Data Management Plan (DMP, Version 1.0 dated on 02 November 2022).

This SAP (Methods) documents the planned statistical analyses and data presentations for the final analysis of study DMVT-505-4001. This SAP will be finalized and approved prior to the database lock. Any deviations from this plan will be documented in the clinical study report (CSR).

# 2. STUDY OBJECTIVES

## 2.1. **Primary Objective**

The primary objective of the study is to evaluate the efficacy of VTAMA (tapinarof) cream, 1% in adults with intertriginous PSO.

## 2.2. Secondary Objectives

The secondary objective of the study is to assess onset of effect of VTAMA (tapinarof) cream, 1% in adults with intertriginous PSO.

[figure not shown]
## 2.4. Safety Objectives

[figure not shown]
The safety objective of the study is to evaluate the safety and tolerability of VTAMA (tapinarof) cream, 1% in adults with plaque PSO in intertriginous areas.

# 3. STUDY DESIGN

### 3.1. Overall Design

This is a single-group, open-label, multicenter study to evaluate the safety and efficacy of VTAMA (tapinarof) cream, 1% in the treatment of plaque PSO in intertriginous areas. Participants will treat plaque PSO in intertriginous areas with VTAMA (tapinarof) cream, 1% QD for 12 weeks. Efficacy of the treatment of plaque PSO in intertriginous areas will be assessed with a PGA evaluation only of intertriginous areas (iPGA).

Study duration:

- The study duration will be up to 17 weeks.
- The treatment duration will be up to 12 weeks.
- The follow-up period will be up to 1 week.

#### **3.2.** Study Assessments

Please refer to protocol Section 8 for descriptions of study procedures and assessments and protocol section 1.3 for timing of procedures and assessments (Schedule of Activities).

### **3.3.** Assignment to Study Intervention

All subjects will be assigned to the study intervention of VTAMA (tapinarof) cream, 1% in the treatment of plaque PSO in intertriginous areas.

## 3.4. Blinding

This is an open-label study.

### 4. SAMPLE SIZE DETERMINATION

The sample size for this study is based on clinical considerations only. No formal sample size calculation will be performed. This study will enroll approximately 30 participants which is considered adequate to evaluate the efficacy and safety for the treatment of plaque PSO in the intertriginous areas.

# 5. STATISTICAL CONSIDERATIONS

### 5.1. General Considerations

will perform the statistical analysis of the data. SAS version 9.4 or higher will be used to generate all statistical outputs (tables, listings, figures [TLFs], and datasets). The International Council for Harmonisation (ICH) numbering convention will be used for all TLFs. Continuous endpoints will be summarized by presenting the number of observations, means, standard deviations, medians, minimums, and maximums. The 95% confidence intervals will be reported as appropriate.

Time to event analyses will use the Kaplan-Meier product limit method (if estimable) based on observed cases.

Categorical endpoints will be summarized by presenting counts and percentages of subjects in corresponding categories. All possible categories as defined in the case report form (CRF) will be populated, even if they have zero counts. With the exception of ethnicity and race in the demographic table, percentages for missing values are omitted and do not account for the percent calculation of other categories. In certain tables (e.g., TEAEs), the total number of subjects is used as denominator. Footnotes will specify the percent basis in those cases.

Individual subject data obtained from the eCRFs and any derived data will be presented by subject in data listings.

### 5.2. Analysis Populations

The intent-to-treat (ITT) population will include all participants enrolled in the study.

#### 5.3. Analysis Windowing

Study days are measured from date of first dose of study medication. Study days corresponding to measurements are calculated as:

- Assessment date date of first dose + 1 if assessment date is on or after the date of first exposure of treatment.
- Assessment date date of first dose if assessment date is before the date of first exposure of treatment.

All efficacy and safety endpoints will be analyzed according to the nominal visits (i.e. actual visit) except for assessments collected on early termination and unscheduled visits. Early termination and unscheduled visits will be re-numbered to an analysis visit based on their windowed visits defined by actual study day. If more than one visit occurs within a single visit window, then the analysis will take the one closest to the target day. If the 2 visits are equidistant from the target day, the visit with later date and time will be used.

Analysis Visit	Target Day	Analysis Visit Window
Baseline (1)	1	1
Week 1	8	Post first dose to Day 12
Week 2	15	Day 13 – Day 22
Week 4	29	Day 23 – Day 36
Week 6	43	Day 37 – Day 50
Week 8	57	Day 51 – Day 71
Week 12	85	Day 72 – Maximum (last day of treatment + 3 days, Day 87)
Week 13	92	> Maximum (last day of treatment + 3 days , Day 87)

The following analysis visit windows will apply to early termination and unscheduled visits:

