7.2 Participant Discontinuation/Withdrawal from the Study

- A participant may withdraw from the study at any time at the participant's own request for any reason (or without providing any reason).
- A participant may be withdrawn at any time at the discretion of the Investigator for safety or compliance reasons.
- At the time of discontinuing from the study, if possible, an early discontinuation visit should be conducted, as shown in the SoA. See SoA for data to be collected at the time of study discontinuation and follow-up and for any further evaluations that need to be completed.
- The participant will be permanently discontinued from the study product and the study at that time.
- If the participant withdraws consent for disclosure of future information, the Sponsor may retain and continue to use any data collected before such a withdrawal of consent.
- If a participant withdraws from the study, the participant may request destruction of any samples taken and not tested, and the Investigator must document this in the site study records.

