#### 5.6. Missing Data

Every effort will be made to collect complete data at all visits.

All efficacy data will be summarized based on observed cases (OC).

Imputation of Missing Efficacy Data

In addition to the efficacy analysis based on OC, the primary and exploratory efficacy endpoints will also be summarized utilizing the last observation carried forward (LOCF) method to impute missing data

Baseline will not be used when applying LOCF and LOCF will be

implemented through Week 12 (i.e., Week 13 not included in LOCF). LOCF summaries will be considered supportive.

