## 7.2. Efficacy Analyses

[figure not shown]
Categorical endpoints will be summarized by presenting counts and percentages of subjects in corresponding categories. Percentages for missing values are omitted and do not account for the percent calculation of other categories. 95% confidence intervals will be presented.

Continuous endpoints will be summarized by presenting the number of observations, means, standard deviations, medians, minimums, maximums, and 95% confidence intervals.

The Kaplan-Meier product limit method will be used to estimate the median time to achieving an iPGA score of 0 or 1 with a  $\geq$  2-grade improvement from Baseline,

Categorical endpoints include:

• Percentage of participants who achieve an iPGA score of clear (0) or almost clear (1) with a ≥ 2-grade improvement from Baseline

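### Must the SAP state which iPGA records feed the LOCF summary, given the closest-to-target rule for visit windows?

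*SAP*

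**What the plan says.** SAP 5.3 (Analysis Windowing) states that efficacy and safety endpoints "will be analyzed according to the nominal visits (i.e. actual visit) except for assessments collected on early termination and unscheduled visits". For those exceptions, "Early termination and unscheduled visits will be re-numbered to an analysis visit based on their windowed visits defined by actual study day". The window table, introduced as applying to early-termination and unscheduled visits, sets these targets and windows:

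- Week 1: Day 8, from after the first dose to Day 12
- Week 2: Day 15, Days 13-22
- Week 4: Day 29, Days 23-36
- Week 6: Day 43, Days 37-50
- Week 8: Day 57, Days 51-71
- Week 12: Day 85, from Day 72 to the later of Day 87 and three days after the last treatment day

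Where a window holds several visits, "If more than one visit occurs within a single visit window, then the analysis will take the one closest to the target day"; a tie goes to the later one.

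SAP 5.6 (Missing Data) bases all efficacy summaries on observed cases and adds that "the primary and exploratory efficacy endpoints will also be summarized utilizing the last observation carried forward (LOCF) method to impute missing data". The readable text breaks off there without a full stop. It resumes by excluding Baseline from LOCF and ending LOCF at Week 12, and it closes with "LOCF summaries will be considered supportive". Protocol 9.3.1 breaks off at the same words.

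SAP 7.2 says of categorical endpoints: "Percentages for missing values are omitted and do not account for the percent calculation of other categories". Protocol 7.2 asks for an exit visit: "At the time of discontinuing from the study, if possible, an early discontinuation visit should be conducted, as shown in the SoA".

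**The concern.** The windowing rule covers all efficacy endpoints and makes no exception for LOCF. A programmer could therefore build the one-record-per-window dataset first and run LOCF on it. Take a participant with baseline iPGA 3, a scheduled Week 8 visit on Day 57 scored 1, and an early-termination visit on Day 68 scored 3. Both visits lie in Days 51-71, at distances of 0 and 11 days from target. Day 57 is kept and Day 68 is dropped. Week 12 is then filled from Day 57, so the participant counts as a responder although the last score seen was a non-response. The opposite error is equally possible.

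The stake is that someone who leaves before Day 72 has no Week 12 value and drops out of the observed-case percentage. In the readable text, LOCF is the only Week 12 responder summary that counts this person. Two programmers could report different LOCF rates from the same data.

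A related uncertainty is whether an unscheduled visit nearer to target may displace the scheduled visit in the same window, or whether the closeness rule only chooses among early-termination and unscheduled records.

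**Working it through.** The plan gives no figure to reproduce: SAP 4 has no sample-size calculation and SAP 5.4 has no hypothesis. The check is a count over the SAP 5.3 window table.

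**Inputs.** Targets and windows come from SAP 5.3, and the planned size of about 30 from SAP 4. Visit tolerances and a dropout rate are not readable in the documents, so drift and dropout below are assumptions.

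**Rule applied.** An early-termination score on day d is lost when the scheduled visit of that window has already taken place and is strictly closer to target. With scheduled visits exactly on target:

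| Window | Exit days on which the score is lost | Count |
|---|---|---|
| Week 1 | 9-12 | 4 |
| Week 2 | 16-22 | 7 |
| Week 4 | 30-36 | 7 |
| Week 6 | 44-50 | 7 |
| Week 8 | 58-71 | 14 |
| Week 12 | none (Days 72-84 are kept) | 0 |

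Total: 4 + 7 + 7 + 7 + 14 = 39. Days 2 to 84 give 83 possible exit days, so the share is 39/83 = 47%. Leaving out the five scheduled days (8, 15, 29, 43, 57) gives 39/78 = 50%.

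**Age of the carried score.** The gaps in days run 1-4 in Week 1, 1-7 in each of Weeks 2, 4 and 6, and 1-14 in Week 8. Their sum is 10 + 28 + 28 + 28 + 105 = 199, so the mean is 199/39 = 5.1 days; the median is 4 and the maximum 14. The gap is 7 days or more on 3 + 8 = 11 of the 39 days, and 8 of those 11 lie in the Week 8 window.

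**Drift in scheduled visits (assumed; denominator 78).** The answer depends on how the closeness rule is read.

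- If scheduled and early-termination visits compete on closeness, the mean share is 45.7%, 42.3% and 38.8% for drift of up to 1, 2 and 3 days. The lowest single pattern is 23/78 = 29%, with every visit 3 days early.
- If the scheduled visit always prevails, the mean stays near 50%. With every visit 3 days late, 1 + 4 + 4 + 4 + 11 = 24 days are lost (24/78 = 31%). With every visit 3 days early, 6 + 10 + 10 + 10 + 17 = 53 are lost (53/78 = 68%).

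**Effect on the LOCF rate.** One reclassified participant moves it by 1/30 = 3.3 points if all 30 are in the denominator. For illustration, 18/30 = 60.0% (exact 95% CI 40.6 to 77.3) becomes 17/30 = 56.7% (37.4 to 74.5). With assumed dropout of 5% to 20%, exit visits for all who leave, and exit days spread evenly, the number of dropped scores is 30 × 0.05 × 39/83 = 0.7 to 30 × 0.20 × 39/83 = 2.8. Only those whose dropped and carried scores fall on opposite sides of the responder boundary would change class, and the documents give no basis for that proportion.

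**Effect on the other summaries.** For an exit before Day 72, Week 12 is missing in the observed-case analysis on either reading. For an exit on Days 72-84, the score falls in the Week 12 window with no scheduled visit to compete with, so it is kept. SAP 5.1 bases the time-to-event analysis on observed cases, so LOCF plays no part there.

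**The case for a change.** The strongest case for a change is that both readings are defensible, they can give different numbers, and one sentence would settle the matter without new data. The lost score would also be the exit score, in the one Week 12 responder summary that covers people who leave. That much is correct: the readable text names no source for LOCF, and the day counts hold.

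Several points weaken it.

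- SAP 5.6 names the method and does not point to SAP 5.3. The last observation, in plain words, is the exit score. The harmful result arises only if an analyst places the one-record-per-window selection ahead of LOCF.
- The gap in the text sits inside the very sentence at issue. It may hold the source rule or something unrelated, such as endpoint names. Silence can be asserted only for the readable text.
- The 47% or 50% treats exit days as evenly spread over the calendar, which nothing in the documents supports. The drift figures shift with the reading chosen.
- A clarifying sentence would itself have to decide whether scores taken after treatment stopped are eligible, so it is not wholly free of choices.

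The related uncertainty reaches a little further. If a participant had both a scheduled Week 12 visit and an unscheduled iPGA nearer to Day 85 in the same window, the observed-case Week 12 value could depend on the reading. But SAP 5.3 opens by analysing scheduled visits under their nominal label and introduces the windows for the other visits only. An analyst following that order would keep the scheduled visit. This too is a clarification and not an error.

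**Conclusion.** No change to the plan is needed. What remains is an unspecified programming input to a summary that the SAP itself ranks as supportive, in a single-arm descriptive study with no test that could be affected. The ordinary reading of the method's name gives the sensible answer. The observed-case Week 12 rate does not depend on the choice for exits before Day 72, and individual data are listed by participant (Protocol 9, SAP 5.1), so a score left out of the LOCF table would still be visible.

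If LOCF were run on the windowed records, the exit score would be lost on 39 of 83 calendar days with on-target visits, and the carried score would typically be a few days older (median 4). The rate would move by 3.3 points per reclassified participant, in no fixed direction. Under an assumed dropout of 5% to 20%, roughly 0.7 to 2.8 scores would be dropped, with fewer changes of class. These sizes rest on evenly spread exit days, an exit visit for everyone who leaves, and all 30 participants in the denominator. The total shift cannot be known from the documents.

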### 5.4. Statistical Hypotheses

Not applicable. Demographic and baseline characteristics, efficacy, safety,

will be summarized descriptively. No inferential

testing will be performed.

## 5.5. Multiplicity Adjustment

Not applicable

#### 5.6. Missing Data

Every effort will be made to collect complete data at all visits.

All efficacy data will be summarized based on observed cases (OC).

Imputation of Missing Efficacy Data

In addition to the efficacy analysis based on OC, the primary and exploratory efficacy endpoints will also be summarized utilizing the last observation carried forward (LOCF) method to impute missing data

Baseline will not be used when applying LOCF and LOCF will be

implemented through Week 12 (i.e., Week 13 not included in LOCF). LOCF summaries will be considered supportive.

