9.3 Statistical Analyses

9.3.1 General Considerations

This study is intended to show that VTAMA (tapinarof) cream, 1% has a favorable safety and efficacy profile when applied to intertriginous areas over a 12-week dosing period.

Objectives and endpoints are provided in Section 3.

Every effort will be made to collect complete data at all visits. All efficacy data will be summarized based on OC. The primary and exploratory efficacy endpoints will also be summarized utilizing the last observation carried forward method to impute missing data

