## 7. EFFICACY ANALYSES

All efficacy analyses will be performed based in the ITT population.

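### The lead Week 12 response rate is an observed-case percentage, and no visible summary gives responders over all ITT participants with a confidence interval

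*SAP*

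**What the plan says.** SAP 7.1 defines the primary endpoint as the percentage of participants with an iPGA of 0 or 1 and at least a 2-grade improvement at Week 12. Five rules decide who is in that percentage.

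- **Population.** SAP 5.2: "The intent-to-treat (ITT) population will include all participants enrolled in the study". SAP 7: "All efficacy analyses will be performed based in the ITT population".
- **Data used.** SAP 5.6: "All efficacy data will be summarized based on observed cases (OC"). Protocol 9.3.1 has the same rule: "All efficacy data will be summarized based on OC".
- **Denominator.** SAP 7.2: "Percentages for missing values are omitted and do not account for the percent calculation of other categories". SAP 5.1 has the same rule and adds that certain tables, with TEAEs as the example, use the total number of subjects. SAP 7.2 carries no such exception.
- **Imputation.** LOCF is added for the primary and exploratory endpoints, but "LOCF summaries will be considered supportive" and "Baseline will not be used when applying LOCF" (both SAP 5.6).
- **Visit assignment.** SAP 5.3: "Early termination and unscheduled visits will be re-numbered to an analysis visit based on their windowed visits defined by actual study day". The Week 12 window for these visits opens on Day 72.

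The sentence that introduces LOCF stops without a full stop just after it mentions imputing missing values. It does so in protocol 1.1, protocol 9.3.1 and SAP 5.6. Text has evidently been removed there.

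**The concern.** This is a single-arm, descriptive study of about 30 people. With no comparator, the absolute Week 12 rate and its interval are the primary result, and the denominator acts on them directly.

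Neither document calls observed cases the lead analysis in so many words. That status follows because all efficacy data are summarised that way and LOCF is labelled supportive. A participant who is in ITT but has no Week 12 iPGA is then inside the named population and outside the headline percentage. That includes anyone whose early-termination visit falls before Day 72, because the visit is assigned to an earlier week.

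Leaving may be related to response. Protocol 5.2 says that participants who need a prohibited medication, a list that includes other psoriasis treatments, may be discontinued, and protocol 7.2 allows withdrawal for safety or compliance. These are plausible routes by which poor responders could leave. The documents do not show that they will be used that way.

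**Working it through.** **Plan's own figure.** The only number is about 30 participants, set without a formal calculation (protocol 9.5, SAP 4). No dropout rate or expected response rate is given, so there is nothing to reproduce.

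**Assumptions.** N = 30 enrolled; m = 1, 3 or 6 missing at Week 12; observed response rate from 40% to about 75%. Intervals are exact (Clopper-Pearson) 95%, also an assumption, because the SAP names no method.

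**Step 1: gap when missing is counted as not achieved.** With x responders among the 30 − m observed:

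x/(30 − m) − x/30 = [x/(30 − m)] × (m/30), that is, the observed-case (OC) rate times the missing share.

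- At exactly 40%: 0.40 × 1/30 = 1.3 points; 0.40 × 3/30 = 4.0; 0.40 × 6/30 = 8.0.
- With whole participants near 40% and near 75%:

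| Missing | OC | All ITT, missing = not achieved | Gap (points) |
|---|---|---|---|
| 1 | 12/29 = 41.4% (23.5–61.1) | 12/30 = 40.0% (22.7–59.4) | 1.4 |
| 3 | 11/27 = 40.7% (22.4–61.2) | 11/30 = 36.7% (19.9–56.1) | 4.1 |
| 6 | 10/24 = 41.7% (22.1–63.4) | 10/30 = 33.3% (17.3–52.8) | 8.3 |
| 1 | 22/29 = 75.9% (56.5–89.7) | 22/30 = 73.3% (54.1–87.7) | 2.5 |
| 3 | 20/27 = 74.1% (53.7–88.9) | 20/30 = 66.7% (47.2–82.7) | 7.4 |
| 6 | 18/24 = 75.0% (53.3–90.2) | 18/30 = 60.0% (40.6–77.3) | 15.0 |

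With m = 0 the two rates are identical.

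**Step 2: direction against full follow-up.** If k of the m missing would have responded, the full-follow-up rate is (x + k)/30. For 18/24 observed and six missing, OC minus that rate is:

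| k | 0 | 1 | 2 | 3 | 4 | 5 | 6 |
|---|---|---|---|---|---|---|---|
| Points | +15.0 | +11.7 | +8.3 | +5.0 | +1.7 | −1.7 | −5.0 |

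Break-even is where the missing respond at the OC rate (6 × 0.75 = 4.5 people). At k = 5, for example, 23/30 = 76.7%, and OC at 75.0% is 1.7 points too low.

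**Step 3: what LOCF recovers.** If all six have a post-baseline non-response, LOCF gives 18/30 = 60.0%, the same as the all-ITT rate. Otherwise it can differ. Assume 15 responders among 24 observed, four of the six missing with an earlier post-baseline iPGA, and two with none:

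- OC: 15/24 = 62.5%.
- LOCF: from 15/28 = 53.6% (no carried responses) to 19/28 = 67.9% (four carried responses).
- All ITT: 15/30 = 50.0%.

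LOCF still leaves out two people, and it exceeds OC if all four carried values are responses.

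**The case against.** **Observed cases are prespecified.** This stands. Protocol 9.3.1 sets the rule and the SAP follows it. A reader might infer that an ITT population and an observed-case percentage contradict each other. They do not: ITT says whose data are eligible, and the observed-case rule says which values are counted. The choice is weak, not inconsistent.

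**A reader can rebuild the all-ITT rate.** Largely true. The response count (protocol 9.3.2), the ITT number (SAP 6.1) and the listings by participant (protocol 9, SAP 5.1) are all planned. What is missing is that rate as a planned result with its interval.

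**An all-ITT rule may sit in the removed text.** This stands and limits confidence. The observed-case, denominator and supportive-LOCF statements are legible. The absence of a further rule can be asserted only for the visible text.

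**Counting missing as not achieved is also an untestable assumption.** True. In the six-missing example, if four or five would have responded, that rate (60.0%) is 13.3 or 16.7 points too low (against 22/30 = 73.3% or 23/30 = 76.7%), while OC is within 1.7 points. A reader might infer that observed cases must overstate the effect; step 2 shows that the direction depends on who leaves. This argues for showing the all-ITT rate beside OC rather than displacing OC.

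**The gaps lie within sampling error.** The intervals do overlap heavily; for 18/24 the half-width is about 18 points. But a shift from selective denominators is not sampling error, and the interval does not account for it.

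**Few may be lost.** Possible. An early-termination iPGA from Day 72, within the Week 12 window, keeps a leaver in. Protocol 7.2 asks for an early discontinuation visit where possible; an iPGA recorded there would feed LOCF.

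**Conclusion.** The point holds for the visible text, with moderate confidence. The headline Week 12 rate excludes enrolled participants without a Week 12 iPGA, supportive LOCF closes the gap only in part, and no visible summary reports responders over all ITT with an interval.

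Its size cannot be fixed from the documents. Under the assumptions above, the gap to the missing-as-not-achieved rate runs from about 1.3 points (one missing, 40% observed) to 15 points (six missing, 75% observed). No hypothesis is tested, so the consequence is for the estimate and its interval, not for error rates or power.

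**What to change.** In SAP 5.6 and 7.2, add a prespecified summary of the primary endpoint: responders divided by all ITT participants, with a missing Week 12 iPGA counted as not achieved and an exact (Clopper-Pearson) 95% interval. Give it at least equal prominence to the observed-case result, keep LOCF as supportive, and print the number missing at Week 12 beside each. Record the addition in SAP 11.1, since protocol 9.3.1 specifies observed cases and LOCF. If the removed text already contains such a rule, the sponsor need only confirm it and its prominence.

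The cost is one table row and some SAP wording, with no new data. The added rate will equal the observed-case rate or be lower, and it is conservative if some of those who leave would have responded.
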